5.7 Dosing Delays / Modifications

During treatment with Dex, any interruption in treatment due to treatment toxicity for greater than 2 weeks will result in removal from study. No dose modifications are otherwise allowed.

During treatment with Enza, patients will remain on study for three months, regardless of dose intensity, treatment modifications or delays. While the standard dose of 160mg by mouth daily is initiated, the investigator may dose adjust for toxicities and interactions per standard protocols for Enza. These dose delays and modifications will be tracked and reported.

6. STUDY ACTIVITIES

6.1 Screening

All patients must sign a written informed consent form before study specific screening procedures are performed. Screening procedures to evaluate patient eligibility for the study will be conducted within 28 days prior to Cycle 1 Day 1. Prior to enrollment, patient must have documented insurance coverage demonstrating ability to pay for Enza. If the patient meets eligibility and screening requirements he will be initiated on study. All required screening, treatment and post-treatment study procedures and assessments must be done within 7 days (+/-) of the specified study visit date.

6.1.1 Screening studies (Screening assessments must begin within 28 days prior to Cycle 1, Day 1)

- Comprehensive medical history and physical exam, including height and weight, and medications.
- ECOG Performance status (PS)
- CBC (Complete blood count) with differential and platelet count
- CMP (Comprehensive Metabolic Panel - Sodium, Potassium, Chloride, BUN, Serum Creatinine, Calcium, Total Protein, Albumin, Total Bilirubin, AST, ALT, Alkaline Phosphatase, HCO₃)
- Serum PSA
- Serum testosterone
- Hemoglobin A1C
- Staging imaging with CT if not already performed within 4 weeks and bone scintigraphy if not already performed within 8 weeks

6.2 Treatment Period

Patients will have continuous treatment of outpatient therapy. Patients who are not surgically castrated will continue to receive ongoing GnRH agonist or antagonist therapy as prior. Patients will be assessed every 1-3 cycles at a clinic visit.

6.2.1 Cycle 1 Day 1 visit:

- Physical exam, including weight, ECOG performance status, vital signs
- CBC (Complete blood count) with differential and platelet count (Not needed if performed within the last 2 weeks at screening)
- CMP (Comprehensive Metabolic Panel - Sodium, Potassium, Chloride, BUN, Serum Creatinine, Calcium, Total Protein, Albumin, Total Bilirubin, AST, ALT, Alkaline Phosphatase, HCO₃) (Not needed if performed within the last 2 weeks at screening)
- Serum PSA
- Hemoglobin A1 (Not needed if performed within the last 2 weeks at screening)
- Blood drawn for to assess level of full length and androgen receptor variant in circulating tumor cells (CTC AR-V7)

- Quality of life surveys (FACIT-Fatigue Scale, RANDSF-36)

6.2.2 Ongoing assessments while on Dex

- Clinic visit after cycle 1 and then every third cycle for patients who are responding after 2 cycles.
 - Physical exam, including weight, ECOG performance status, vital signs
 - Assessment of toxicity
 - Quality of life surveys
- PSA every cycle
- CBC, Comprehensive Metabolic Panel, Hemoglobin A1c every 3 cycles
- CT scan and bone scan every 3 cycles
- Blood drawn for research testing to assess level of full length and variant androgen receptor at time of progression on Dex (at time of initiation of Enza).

6.2.3 Ongoing assessment while on Enza

- Clinic visit every cycle.
 - Physical exam, including weight, ECOG performance status, vital signs
 - Assessment of toxicity
 - Quality of life surveys
- PSA every cycle

6.3 End of Study

- Clinic visit
 - Physical exam, including weight, ECOG performance status, vital signs
 - Assessment of toxicity
 - Quality of life surveys
- PSA
- CBC, Comprehensive Metabolic Panel, Hemoglobin A1C
- CT scan and bone scan

6.4 Early Discontinuation

- Clinic visit
- If early discontinuation is due to an adverse event or toxicity of any of the study treatments, the patient should be followed until resolution of the adverse event/toxicity or at least one month, whichever is later.

7. SAFETY AND ADVERSE EVENTS

Safety will be evaluated based on the incidence, severity, duration, causality, seriousness, and type of adverse events (AEs), and changes in the patient's physical examination, vital signs, and clinical laboratory results. Investigators will use the NCI CTCAE version 4.0 published 28 May 2009 to assess the severity of adverse events and toxicities (see Appendix B). All observed or volunteered adverse events regardless of treatment group or causal relationship to study drug will be recorded on the adverse event pages of the case report form.

8. PHARMACEUTICAL INFORMATION

8.1 Enza

8.1.1 Administration

Enza 160 mg daily (the current FDA approved dose), or four 40 mg capsules by mouth daily, will be administered. A 30 day supply will be prescribed at the beginning of each month. The study will not pay for supply of Enza.

8.1.2 Supply

Enza, marketed as Xtandi, comes in 40 mg capsules and are supplied as white to off-white oblong soft gelatin capsules imprinted in black ink with MDV. Enza capsules are available in bottles of 120 capsules (NDC 0469-0125-99).

8.1.3 Storage

Store Enza capsules at 20°C to 25°C (68°F to 77°F) in a dry place and keep the container tightly closed. Excursions permitted from 15°C to 30°C (59°F to 86°F).

8.2 Dex

8.2.1 Administration

Dex 2 mg daily by mouth will be administered.

8.2.2 Supply

Dex, marketed as Decadron, comes in 2 mg tablets in generic formulations. A 90 day supply will be prescribed every 3rd cycle.

8.2.3 Storage

Store Dex tablets at 20° to 25°C (68° to 77°F). Protect from moisture.

9. STUDY CALENDAR

Baseline screening evaluations are to be conducted within 28 days prior to Cycle 1, Day 1. Cycles are 28 days. Return visits after initiation of therapy can be done within 7 days (+/-) of the specified study visit date.

	Screening ¹	Dex C1	Dex C2	Dex C3	Dex C4 -> ongoing	Progression (post Dex)	Enza C1	Enza C2	Enza C3 (Study Conclusion Visit)
Dex		X	X	X	X				
Enza							X	X	X
Informed consent	X								
Demographics	X								
Medical history	X								
Concurrent meds	X	X	X	X	X	X	X	X	X
Physical exam	X	X	X	X	X	X	X	X	X
Vital signs ⁸	X	X	X	X	X	X	X	X	X
Height	X								
Weight	X	X	X	X	X	X	X	X	X
Performance status	X	X	X	X	X	X	X	X	X
CBC w/diff, plts ²	X	X ⁴		X	X ⁶	X			X
Serum chemistry ³	X	X ⁴		X	X ⁶	X			X
Hemoglobin A1C	X	X ⁴		X	X ⁶	X			X
PSA	X	X	X	X	X	X	X	X	X
Serum testosterone	X								
Adverse event evaluation		X	X	X	X	X	X	X	X
CT Scan (C/A/P)	X ⁹			X ⁵	X ⁶	X			X
Bone Scan	X ⁹				X ⁶				X
QOL (FACIT, RAND SF-36)		X	X	X	X	X	X	X	X
AR-V7 CTC measurement		X ⁷				X ⁷			

1 Screening assessments must begin within 28 days prior to Cycle 1, Day 1

2 CBC (Complete blood count) with differential and platelet count

3 CMP (Comprehensive Metabolic Panel - Sodium, Potassium, Chloride, BUN, Serum Creatinine, Calcium, Total Protein, Albumin, Total Bilirubin, AST, ALT, Alkaline Phosphatase, HCO₃)

4 Not needed if performed within the last 2 weeks at screening

5 CT scan post-cycle 2 on Dex if evidence of PSA progression

6 CBC, CMP, Hgb A1C and Radiologic Evaluation (CT scan, bone Scan) will be performed every 3 cycles while responding to Dex.

7 Blood Samples for assessment of AR and AR-V expression will be taken at baseline and at time of initiation of Enza.

8 Vital signs: Temperature, blood pressure and pulse rate will be measured.

9 Screening Radiologic Evaluation with CT of the chest, abdomen and pelvis within 4 weeks and bone scan within 8 weeks prior to C1 D1.

10. STUDY ASSESSMENTS

10.1 Assessing PSA response

PSA response and progression will be defined per PCWG2 criteria (Appendix E). PSA response is defined as a 50% decline in baseline PSA. PSA progression is defined as an elevation of 25% and an absolute increase of at least 2ng/dl over the nadir, confirmed by a second measurement at least 3 weeks apart. Patients will have PSA measurements taken every cycle of therapy.

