Treatment Plan: Patients will be prescribed Dex 2mg tablets to take daily by mouth with food. All patients will receive a minimum of two months of Dex. Following PSA or radiographic progression of disease, patients will be prescribed Enza 160 mg (40 mg tablets x4) by mouth daily. Dex will be tapered and stopped over a one week period. Enza will be continued for three months, after which time patients will be assessed for response. All patients will come off study after 3 months of Enza. Patients without evidence of response to Enza will be offered other standard of care therapy or additional clinical trial. Patients demonstrating Enza response will come off trial and be allowed to continue Enza as standard of care therapy. Blood Samples for assessment of AR and AR-V expression will be taken at baseline and at time of initiation of Enza.

Assessment of Response: Patients will have monthly PSA measurements. Disease will be assessed with bone scan and CT C/A/P at baseline, prior to initiation of Enza and at study conclusion. Progression will be defined by RECIST 1.1 and PCWG-2 criteria for soft tissue and bone metastasis, respectively. PSA response will be defined as 50% decrease in PSA from initiation of Enza. PSA progression will be defined by PCWG-2 criteria.

Rationale: The treatment options are very limited for patients with metastatic prostate cancer whose disease has become resistant to hormonal therapy and chemotherapy. Initially, the disease responds to drugs such as Enza, which block the androgen receptor. However, prostate cancer becomes resistant to this therapy through several mechanisms, including changes in the cancer's expression of the androgen receptor.

Dex and other glucocorticoids are an established treatment for prostate cancer; they can provide pain control, relief of other cancer-related symptoms like anorexia and fatigue, as well as have a direct anti-cancer effect. The receptor for glucocorticoids is expressed on many advanced prostate cancers, and recent work has theorized that there is interaction between the glucocorticoid receptor and androgen receptor pathways. It is thought that using a drug to affect one of the receptors may change the expression patterns and signaling of the other receptor.

Given that Dex has a known benefit, and that there is a likely interaction between the androgen

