1.2 Secondary Objectives

- 1.2.1 Objective response rate to Enza in patients with measurable disease on CT scan using RECIST criteria.
- 1.2.2 Time to PSA progression (based upon PCWG2 criteria) for treatment with Dex.
- 1.2.3 Effect of each treatment on quality of life as assessed by patient completion of validated instruments (FACIT-Fatigue Scale, RANDSF-36) Quality of life assessments will be taken at study entry, during second on-treatment visits for both Dex and after 3 cycles of Enza.
- 1.2.4 PSA response rates to Dex for patients who are AR-V7 positive and AR-V7 negative, respectively, at study entry.
- 1.2.5 Response rates to Enza for patients who are AR-V7 positive and AR-V7 negative, respectively, at study entry.
- 1.2.6 Percentage of patients who are AR-V7 positive at study entry who are AR-V7 negative at time of initiation of Enza, or vice-versa.

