5.2.1 Study Treatments

[figure not shown]
Patients will continue on ADT with LHRH agonist (i.e. Zoladex, Trelstar, Eligard or Lupron) or LHRH antagonist (Degarelix) if not surgically castrated throughout the duration of the study.

Patients will be prescribed Dex 2mg tablets to take once daily orally with food for 28 days/cycle continuously. Patients who have PSA progression after one cycle will continue on Dex for a second cycle. Patients with continued increase in PSA (if satisfies progression based upon PCWG2 definition) will begin Enza. Patients with declining PSA after 2 cycles of Dex will continue on Dex until PSA progression. Every 3 cycles patients will have repeat bone/CT scans to evaluate treatment response. Patients will remain on treatment with Dex until evidence of PSA progression (per the PCWG2 definition) or disease progression on CT scan (per RECIST criteria), or progressive bone metastatic disease (per the PCWG2 definition).

At time of progression, Dex will be stopped via a rapid taper over one week if patients were treated for >30 days. Patients will be instructed to take 1 mg Dex for 7days, then stop. However, ongoing use of corticosteroids will be allowed if indicated for bone pain or adrenal suppression.

Patients will then be prescribed Enza 40 mg tablets and instructed to take 4 tablets per day orally with or without food for 28 days/cycle continuously. Dose adjustments and delays will be allowed as per standard of care with treatment with Enza. Patients will have PSA checked monthly. All patients will remain on Enza for 3 cycles regardless of PSA response. At the end of 3 cycles of Enza all patients will come off study. Those patients with PSA or radiographic progression will come off study and be offered standard of care or another clinical trial. Those patients with PSA or radiographic response after 3 cycles will be offered to remain on Enza as standard of care therapy.

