PSA	Record the percent change from baseline (rise or fall) at 12 weeks, and separately, the maximal change (rise or fall) at any time using a waterfall plot	Decline from baseline: Record time from start of therapy to first PSA increase that is $\geq 25\%$ and ≥ 2 ng/mL above the nadir, and which is confirmed by a second value ≥ 3 weeks later (i.e. a confirmed rising trend). Recording the duration of PSA decline of little value No decline from baseline: PSA progression $\geq 25\%$ and ≥ 2 ng/mL after 12 weeks
Soft-tissue lesions	Use RECIST with caveats Only report changes in lymph nodes that were ≥ 2 cm in diameter at baseline Record changes in nodal and visceral soft tissue sites separately Record complete elimination of disease at any site separately Confirm favorable change with second scan Record changes using waterfall plot	Use RECIST criteria for progression, with additional requirement that progression at first assessment be confirmed by a second scan 6 or more weeks later (particularly important for biologic therapies) Note that for some treatments, a lesion may first increase in size before it decreases
Bone	Record outcome as new lesions or no new lesions First scheduled reassessment: No new lesions: continue therapy New lesions: perform a confirmatory scan 6 or more weeks later Confirmatory scan: No new lesions: continue therapy Additional new lesions: progression Subsequent re-assessments:	The appearance of ≥ 2 new lesions, and, for the first reassessment only, a confirmatory scan performed 6 or more weeks later that shows a minimum of 2 or more additional new lesions The date of progression is the date of the first scan that shows the change

	No new lesions: continue New lesions: progression
Symptoms	Consider independently of other outcome measures Document pain and analgesia at entry with a lead in period and measure repeatedly at 3- to 4-week intervals Perform serial assessments of global changes in HRQOL, urinary or bowel compromise, pain management, additional anticancer therapy Ignore early changes (< 12 weeks) in pain or HRQOL in absence of compelling evidence of disease progression Confirm response or progression of pain or HRQOL end points > 3 weeks later

Abbreviations: PSA, prostate-specific antigen; HRQOL, health-related quality of life

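### Section 10.1 prints the absolute PSA rise for progression as 2 ng/dl where the Appendix E it cites says 2 ng/mL; whether Appendix E's 12-week condition applies during Dex is also left unclear

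*Protocol*

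**What the plan says.** Protocol section 10.1 says that PSA response and progression follow PCWG2 as set out in Appendix E. It then writes the progression rule out: a 25% elevation together with "an absolute increase of at least 2ng/dl over the nadir", confirmed at least 3 weeks later. No other section of the protocol body gives numbers for PSA progression. The synopsis, 1.2.2, 5.2.1 and 12.1 refer to PCWG2, and 12.3 and the SAP name the endpoint without defining it.

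Appendix E has two PSA progression lines. After a decline from baseline, the rise must be at least 25% and at least "2 ng/mL above the nadir, and which is confirmed by a second value". The event is dated at the first such rise: "Record time from start of therapy to first PSA increase that is" of that size. With no decline from baseline, the rise must be at least 25% and "≥ 2 ng/mL after 12 weeks".

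The rule is used in two places:

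- **Switch from Dex to Enza (5.2.1).** "Patients who have PSA progression after one cycle will continue on Dex for a second cycle". Then: "Patients with continued increase in PSA (if satisfies progression based upon PCWG2 definition) will begin Enza". The synopsis adds: "All patients will receive a minimum of two months of Dex".
- **Secondary objective 1.2.2.** "Time to PSA progression (based upon PCWG2 criteria) for treatment with Dex", summarised by Kaplan-Meier under 12.3 and the SAP.

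**The concern.** A decision threshold in operative text carries the wrong unit. The absolute floor stops small fluctuations at a low PSA from counting as progression. At one hundredth of its size it no longer does that. A site working from 10.1 alone could stop Dex and start Enza on a rise that Appendix E would not count, and the event time for the secondary endpoint would move with it.

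The second question is timing. Appendix E counts progression in a patient with no PSA decline only after 12 weeks. Section 10.1 has no such condition, and 5.2.1 speaks of PSA progression after one cycle and a possible switch after the second. Two analysts could date the event differently for the same patient.

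**Working it through.** **Inputs.** Relative rise 25% and absolute rise 2 ng/dl (10.1); absolute rise 2 ng/mL and the 12-week condition (Appendix E); 28-day cycles with PSA every cycle (section 9 and 10.1).

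**The plan's own figures.** The two-stage design (stop at 0 of 13, promising at 3 or more of 20) reproduces.

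- Early stopping at a 5% rate: 0.95^13 = 0.513 (stated 0.51).
- Probability of declaring the regimen promising: the sum over x = 1 to 13 of P(X1 = x) × P(X2 ≥ 3 − x), with X1 binomial on 13 and X2 binomial on 7. This is 0.0736 at 5% (stated limit 0.1) and 0.903 at 25% (stated 90%).

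The PSA progression rule does not enter these calculations.

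**Unit.** 1 dL = 100 mL, so 2 ng/dl = 2/100 = 0.02 ng/mL, and 2/0.02 = 100.

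**Threshold.** For nadir N and absolute rise d, progression needs a PSA of at least max(1.25 × N, N + d). The absolute part governs when d > 0.25 × N, that is, N < d/0.25.

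- As printed: 0.02/0.25 = 0.08 ng/mL.
- Appendix E: 2/0.25 = 8 ng/mL.

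| Nadir (ng/mL) | 10.1 as printed | Appendix E | Rise required |
|---|---|---|---|
| 0.5 | 0.625 | 2.5 | 25% vs 400% |
| 1 | 1.25 | 3.0 | 25% vs 200% |
| 2 | 2.5 | 4.0 | 25% vs 100% |
| 4 | 5.0 | 6.0 | 25% vs 50% |
| 6 | 7.5 | 8.0 | 25% vs 33% |
| 8 | 10.0 | 10.0 | 25% vs 25% |

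For example, at nadir 1: max(1.25, 1.02) = 1.25 against max(1.25, 3) = 3.0. Between nadirs of 0.08 and 8 the gap is 2 − 0.25 × N. It is 1.75 at nadir 1, 1.0 at nadir 4, 0.5 at nadir 6 and zero at 8. A call changes only if a measured PSA falls inside that gap. At nadir 4, a next value of 7 meets both rules at the same visit, whereas a value of 5.5 meets only the printed one.

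**Twelve weeks, patients with no decline, nominal visits.** Cycles 1, 2 and 3 end on days 28, 56 and 84; 84 days = 12 weeks.

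| First qualifying rise, then confirmation | 10.1 without a 12-week condition | 12-week condition applied |
|---|---|---|
| End of cycle 1, then cycle 2 | event day 28, switch day 56 | event and switch day 84 at the earliest |
| End of cycle 2, then cycle 3 | event day 56, switch day 84 | event and switch day 84 at the earliest |

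In the first row the event moves by at least 84 − 28 = 56 days and the switch by at least 84 − 56 = 28 days. In the second the event moves by at least 84 − 56 = 28 days, and the switch need not move.

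**The case against.** On the unit, the strongest reply is that the documents already resolve it. Section 10.1 opens by citing Appendix E, both PSA lines there use ng/mL, and no other section repeats ng/dl. That shows what was meant, and a careful reader would apply 2 ng/mL. It does not make the printed threshold right. The introduction to the Appendix E table also says that the table does not replace the protocol, so a reader who follows that sentence is sent back to the wrong unit.

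A reader might infer that progression is called early in every patient with a nadir below 8 ng/mL. The documents do not support that. PSA is taken once per cycle, and many rises will clear both thresholds at the same visit.

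A reader might also infer that the trial departs from PCWG2 by switching at cycle 2. That goes too far. Section 5.2.1 makes the switch conditional on the PCWG2 definition. The two months of Dex is a minimum, not a trigger. Footnote 5 of the study calendar and section 10.2 call for a CT after cycle 2, not a change of drug. A patient with no decline who has not met the full Appendix E rule could simply stay on Dex.

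The opposite reading is also open: the protocol body governs, 10.1 has no 12-week condition, and the Appendix E introduction says only that PCWG2 was largely followed. Because each reading has support, an ambiguity remains, but a departure is not established.

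**Conclusion.** The unit in 10.1 is wrong as written, with high confidence, and almost certainly a typing slip. Read literally, it lowers the progression threshold for nadirs below 8 ng/mL, by up to 1.75 ng/mL across the tabulated nadirs of 1 and above, and makes no difference from 8 ng/mL up. The documents give no PSA distribution, so the number of patients affected cannot be stated. Nothing in them shows that any site would apply 0.02 ng/mL.

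The 12-week question is an ambiguity, held with lower confidence. On nominal 28-day visits, in the cases worked, the two readings differ by at least 28 or 56 days in event date, and by at least 28 days or possibly not at all in switch date.

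The reach of both is limited to the date of the switch, hence the PSA value that serves as the Enza baseline, and to a descriptive Kaplan-Meier summary in at most 20 patients. It would be wrong to infer that the primary endpoint definition, sample size or power is compromised; none of them uses the progression rule. Severity: minor.

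**What to change.** In 10.1, change the unit of the absolute rise from ng/dl to ng/mL.

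Also in 10.1, state whether the Appendix E 12-week condition applies to patients with no PSA decline on Dex. Use the same rule for the switch in 5.2.1 and for time to PSA progression in 12.3 and the SAP. Either choice is defensible:

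- **If the condition applies,** reword 5.2.1 so that patients with no decline do not switch on PSA alone before day 84. The price is at least 28 more days of Dex for a patient whose rise was confirmed at the end of cycle 2.
- **If it is set aside,** say so, and qualify the PCWG2 references in the synopsis, 1.2.2 and 12.1. The price is that time to PSA progression on Dex is no longer directly comparable with studies that keep the 12-week rule.

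Both changes are wording in a protocol amendment. Neither requires added patients or new types of assessment.

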10.2 Assessing response in measurable disease

In patients with measurable disease, tumor response will be evaluated using CT and bone scan. Patients will undergo screening CT scan and bone scan. CT scan is repeated after 2 cycles of Dex if evidence of PSA progression, otherwise CT and bone scan are performed every 3 months to determine disease response/progression to Dex or Enza. Progression for soft tissue lesions will be based on RECIST 1.1 criteria (Appendix C) and for bone lesions based on PCWG2 criteria.

